Appendix E: Medical Referral Values and Recommended Actions

Evaluation	Findings	Recommended Actions
Blood Pressure	SBP \geq 180 or DBP \geq 110	Seek care as soon as possible as this is a potential emergency health condition. *Based on AHA 2010 guidelines
	SBP 160 to 179 or DBP 100 to 109	See a health care provider within the next month.
	SBP 140 to 159 or DBP 90 to 99	See a health care provider within the next two months.
	SBP 120 to 139 or DBP 80 to 89	Find out from a health care provider if any additional evaluations or lifestyle changes are indicated.
	SBP < 120 AND DPB < 80	No recommendation.
Resting Heart Rate	HR > 120 bpm	See a health care provider as soon as possible.
	101 \leq HR \leq 120 bpm	See a health care provider within the next month.
	40 \leq HR \leq 59 bpm	Participant may want to discuss findings with their health care provider.
	HR < 40 bpm	See a health care provider as soon as possible.
	60 \leq HR \leq 100	No recommendation.
BMI	Obese (\geq 30)	If obese, overweight, or underweight, discuss results and potential lifestyle changes with a health care provider.
	Overweight (25 to 29.9)	
	Normal (18.6 to 24.9)	
	Underweight (< 18.5)	
Spirometry	Either FEV ₁ , FVC, or FEV ₁ /FVC below lower limits of normal AND FEV ₁ , < 50% predicted	See a health care provider within the next week.
	Either FEV ₁ , FVC, or FEV ₁ /FVC below lower limits of normal AND FEV ₁ , \geq 50% predicted	See a health care provider within the next month.

Evaluation	Findings	Recommended Actions
	FEV ₁ , FVC, and FEV ₁ /FVC all above lower limits of normal	No recommendation.
Pulse Oximetry	SpO ₂ between 95%-100% - considered normal range	No recommendation.
	SpO ₂ between 91% - 94% - suggests hypoxemia or other health problem may be present	Participant is advised to discuss findings with their health care provider.
	SpO ₂ < 90% - suggest possible acute respiratory failure	Seek care as soon as possible as this is a potential emergency health condition.

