4.1.4 Reports to Participants and Referrals

During each registry visit, study staff will collect measurements including: height and weight to calculate BMI, blood pressure, pulse oximetry and spirometry. The participant will receive handouts with the results of these tests/measurements, standardized clinical interpretations, and advice for seeking care (see Appendix E: Medical Referral Values and Recommended Actions). In addition to providing the participant with results, handouts and recommended actions, participants who do not have a primary care provider or who cannot afford to pay for care may be referred to a local clinic that provides care for services based on a sliding scale. The referral handout consists of a list of health resources and mental health resources including the DHHS Health Resources and Services Administration (HRSA) "Find a Health Center" search page and the Substance Abuse and Mental Health Services Administration (SAMHSA) treatment facility locator search page.

In the rare event where the clinical exam visit yields immediately actionable medical data (e.g., dangerously low/high blood pressure or O₂ saturation), trained study staff will immediately inform the coordinating center site manager and facilitate, if necessary, the administration of emergency care. The study staff will be responsible for ensuring appropriate follow-up care until the event resolves or stabilizes and the participant is under the care of a licensed medical provider.

It may be many years before participant samples are tested. Participants will not receive individual results from the future analysis of samples unless the analysis yields an abnormal value.

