6.4 Spirometry

Spirometry will be conducted according to American Thoracic Society (ATS) guidelines ([6](#), [7](#)).

Spirometry will be performed using a portable, transit time-based spirometer (e.g., EasyOne, ndd Medical Technologies, Inc., Andover, MA, USA, or a comparable model). All spirometers will undergo standard quality control checks each day they are used. A full Forced Vital Capacity (FVC) maneuver will be conducted to obtain three ATS-acceptable forced expiratory maneuvers, with a maximum of eight attempts allowed.

Spirometry will be conducted with the participant seated and wearing a disposable nose clip. New, individually-packaged, disposable mouthpieces and new spacers will be used for each participant.

To the extent possible, participants will be asked to not use their asthma inhalers on the day of the examination, and the timing and dosage of all asthma medications taken over the preceding seven days will be recorded.

Study staff conducting spirometry will be trained by coordinating center research staff familiar with collecting spirometric data in the field. Following training, staff will be required to submit 5 practice tests that are judged as acceptable by the pulmonary function testing software and will receive certification from coordinating center research staff. If computer-generated quality scores are lower than expected, coordinating center research staff will provide feedback along with suggested corrective actions to the study staff performing spirometry.

Exclusion from Undergoing Spirometry

Participants with a blood pressure >180 mmHg systolic or >110 mmHg diastolic, or with a heart rate >100 or <40 beats per minute will not undergo spirometry during the visit. Additionally, participants who answer yes to any of the following questions will also not be tested:

- In the past three months, have you had any surgery to your chest or abdomen?
- In the past three months, have you had a heart attack or stroke?

- In the past three months, have you had a detached retina or have you had eye surgery?
- In the past three months, have you been hospitalized for any other heart problem?
- Are you currently taking medication for tuberculosis?

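### Appendix E has no row for SpO2 of exactly 90%, conflicts with Section 4.1.4 on low blood pressure, and differs from Section 6.4 at exactly 180 or 110 mmHg

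*Protocol*

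**What the plan says.** Protocol Section 4.1.4 says that each participant receives handouts with results, interpretations and advice on seeking care, and refers to Appendix E for these. A separate paragraph of Section 4.1.4 covers readings that need action on the spot. It gives "dangerously low/high blood pressure" and oxygen saturation as examples. Staff must then tell the coordinating center's site manager at once and help arrange emergency care where needed. That paragraph gives no numeric threshold and does not cite Appendix E.

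Appendix E has three SpO2 rows:
- "between 95%-100% - considered normal range", with the advice "No recommendation";
- "between 91% - 94% - suggests hypoxemia or other health problem may be present", with advice to discuss the finding with a provider;
- "< 90% - suggest possible acute respiratory failure", with the advice "Seek care as soon as possible as this is a potential emergency health condition".

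For blood pressure, the top row starts at 180 systolic or 110 diastolic, both values included, and carries the same advice, "Seek care as soon as possible as this is a potential emergency health condition". The bottom row covers systolic below 120 together with diastolic below 80, has no lower limit, and reads "No recommendation".

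Section 6.4 bars from spirometry "Participants with a blood pressure >180 mmHg systolic or >110 mmHg diastolic", and also anyone with a heart rate above 100 or below 40.

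**The concern.** A referral table works only if each reading leads to one piece of advice and if that advice agrees with the rest of the protocol. Here one SpO2 value next to the most urgent band has no advice. A blood-pressure reading that the body text would call actionable can produce a handout with no recommendation. And a reading labelled a potential emergency does not by itself bar forced expiratory maneuvers, of which Section 6.4 allows up to eight attempts.

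The protocol's structure makes this more than cosmetic. Section 2.3 places the elements expected to stay unchanged in the main body, approved in advance. Appendix D explains that at activation the IRB can confine itself to new material, and its sample checklist records no protocol changes. A slip in the standing text could therefore reach the field handouts of each disaster without a further look. Visits may take place at a staging area before deployment (Section 4.1.2), where staff need rules that they can apply literally.

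**Working it through.** No sample size, power or error rate is involved. The check applies the rows literally to every reading in a range and looks for readings with no row, and for disagreement between sections.

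**Conventions.** SpO2, blood pressure and heart rate are taken as whole numbers and BMI to one decimal; the protocol does not state display precision. The blood-pressure rows join systolic and diastolic limits with *or*, so one pair can meet two rows. They are therefore read from the most severe downward.

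**SpO2, 70 to 100.** The rows cover 95–100, 91–94 and values below 90. The only value left over is 90. The row above it advises a discussion with a provider; the row below it advises seeking care as soon as possible.

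**BMI, 12.0 to 49.9.** The rows are below 18.5, 18.6–24.9, 25–29.9, and 30 and above. The only value left over is 18.5.

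**Blood pressure, systolic 40–259 and diastolic 20–149.** Every pair has a row. Because the bottom row is unbounded, pairs such as 70/40 and 50/30 return "No recommendation". Section 4.1.4 lists dangerously low pressure as immediately actionable. The two cannot both describe the same reading properly, and no number in the protocol says where one stops and the other starts.

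**Appendix E top row against the Section 6.4 exclusion.**

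| Reading | Appendix E top row (≥180 or ≥110) | Section 6.4 exclusion (>180 or >110) |
|---|---|---|
| 179/109 | no | no |
| 180/80 | yes | no |
| 120/110 | yes | no |
| 181/80 | yes | yes |

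On the grid the two rules disagree for 231 pairs, all with systolic exactly 180 or diastolic exactly 110:
- systolic 180 with diastolic 20 to 110: 91 pairs;
- diastolic 110 with systolic 40 to 180: 141 pairs;
- 180/110 is counted twice, so 91 + 141 − 1 = 231.

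This count locates the mismatch. It is not a frequency among participants.

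**Heart rate, 20 to 219, as a comparison.** No value lacks a row. The Section 6.4 limits (above 100, below 40) coincide at every whole number with the Appendix E rows that advise seeing a provider (101–120, above 120, below 40). The heart-rate rows also include an action for low values, which the blood-pressure rows do not.

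**The case against.** The strongest reply is that the protocol does not leave these participants unprotected. A reader might infer that serious readings lead to no action. For blood pressure the documents do not support that. Section 4.1.4 prescribes action for dangerously low or high readings and makes staff responsible until the participant is under licensed care. Section 9.4.7 adds that participants will be told of findings that indicate immediate risk. A reading of exactly 180 or 110 still receives the strongest blood-pressure advice in the table. A reader might also infer that Appendix E governs on-site action, but Section 4.1.4 ties it to the handouts and sets out on-site action separately. This part of the reply stands. What remains is a conflict between handout and body text, a missing threshold, and one SpO2 value without advice. The undefined wording on oxygen saturation may or may not cover that value.

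A second reply is that a referral rule and a procedure exclusion serve different purposes, need not share a cut-off, and can both be followed at once. That is fair, and the two rules are not logically incompatible. But the protocol does not say that the difference is intended, and the heart-rate limits do coincide in the same two places.

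A third reply concerns scale. The registry is described as minimal risk, the core set omits vital signs and oximetry, spirometry belongs to the enhanced set only (Table 1), and results do not decide deployment (Section 6). All of this stands and bears on severity. Nor can it be claimed that rounding makes exact 180 or 110 readings common: the documents give no distribution of readings, and Section 6.1 specifies oscillometric equipment.

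**Conclusion.** The point holds as a set of inconsistencies in a safety-facing table:
- no row for SpO2 of exactly 90%;
- a trivial gap at BMI 18.5;
- handout advice on low blood pressure that conflicts with Section 4.1.4, which itself has no threshold;
- at exactly 180 systolic or 110 diastolic, a potential-emergency label without exclusion from spirometry, and no stated reason for the difference.

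The extent in readings is one SpO2 value, one BMI value, the unbounded lower end of one row, and two boundary values. The number of participants affected cannot be estimated from the protocol and is likely to be small at the exact boundaries. Nothing here touches an endpoint, the sample-size tables or an analysis. The gaps at 90% and 18.5 assume whole-number SpO2 and one-decimal BMI. The low-pressure conflict and the 180/110 mismatch do not depend on that assumption. Should-fix.

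**What to change.** Reconcile Appendix E with Sections 4.1.4 and 6.4:

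1. Rewrite the Appendix E bands so that every possible SpO2, BMI and blood-pressure reading falls in exactly one row. State the display precision, and state which row applies when systolic and diastolic values point to different rows.
2. Make the low-blood-pressure advice in Appendix E consistent with Section 4.1.4, and make clear in Section 4.1.4 which readings its on-site paragraph covers.
3. Handle readings of exactly 180 or 110 consistently in Appendix E and Section 6.4, or state that the difference is intended and why.

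The sponsor's clinical lead sets all values; this review proposes none. The cost is an edit to one appendix and the related sentences, IRB approval of the amendment, and reprinted handouts. It is best done before activation, while the standing text can be amended without delaying a field response.

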Appendix F: Review of RAPIDD Protocol Implementation

The purpose of this worksheet is to evaluate the implementation of the RAPIDD protocol to ensure that the safeguards put in place at the time of original approval are adequate to protect the safety of actual subjects in the specific disaster setting. Based on the type of disaster, this worksheet will provide summary details about enrollment, response rates, adverse events, any new information that may affect risk or benefit to participants, and evaluation of study procedures. This completed worksheet must be submitted to the NIEHS Institutional Review Board **within 60 days** of study protocol implementation. A template outline for the RAPIDD protocol implementation review report is as follows:

- I. Description of study progress (provide a narrative describing the disaster and its impact, the deployment setting, operational environment, etc.):
- II. Evaluation of recruitment and enrollment (provide information about recruitment methods, response rates, subject accrual demographics, summary statistics on enrolled subjects, and evaluation of the enrollment location):
- III. Evaluation of study procedures (provide information about the effectiveness of study operations, study procedures, and whether or not procedures interfered with disaster worker responsibilities):
- IV. Discussion of any new information that may affect risk or benefit to subjects:
- V. Summary of adverse events and any unanticipated problems involving risks to subjects or others:
- VI. Explanation of how this research could benefit the community or our understanding of the community impacts:
- VII. Description of data and safety monitoring plan:
- VIII. List of collaborators and their contributions to success/failure:
- IX. Justification for continued study of enrolled participants based on cumulative results thus far, including new interesting specific endpoints of the study:
- X. Suggested protocol modifications, if applicable:
